## 6.3.2 Serious Adverse Events

The FDA (2009) defines a serious adverse event as an adverse event that: results in the participant's death, is life-threatening, results in hospitalization (initial or prolonged), results in significant, persistent, or permanent change, impairment, damage, disruption, or disability in the participant's body function/structure, physical activities or quality of life, results in a congenital anomaly, or requires intervention to prevent permanent impairment or damage.

#### 6.3.3 Procedures for Serious Adverse Events

There are no expected serious adverse events (SAE) in this study. In accordance with 21 CFR Parts 803 and 812, an SAE is defined as any untoward medical occurrence that: results in death, is lifethreatening, requires inpatient hospitalization or prolongation of existing hospitalization, results in persistent or significant disability/incapacity, is a congenital anomaly/birth defect, or requires intervention to prevent permanent impairment or damage. All SAE will be reported to [name] and the Data Safety Monitoring Board Chair in 24 hours after knowledge of the occurrence.

If a serious adverse event (SAE) occurs during a study visit the study coordinator should first insure the participant receives any needed medical attention. If the study coordinator is notified by phone, the coordinator should confirm that the participant has received medical attention. The study coordinator should then notify the site Principal Investigator and complete the adverse event form. All SAE will be reported to [name] and the Data Safety Monitoring Board in 24 hours after knowledge of the occurrence. Study coordinators should comply with local regulations and policies when notifying the institutional IRB. The DSMB will review all SAEs and the Chairperson of the DSMB will notify the HRPO and principal investigator of adverse safety outcome information sufficient to stop the study.

The principal investigator has the obligation to report all serious adverse events to the FDA, IRB, and Novartis Pharmaceuticals Drug Safety and Epidemiology Department (DS&E). All events reported to the FDA by the investigator are to be filed utilizing the Form FDA 3500A (MedWatch Form), if applicable

To ensure patient safety, every SAE, regardless of suspected causality, occurring after the patient has provided informed consent and until at least 30 days after the patient has stopped study treatment must be reported to Novartis within 24 hours of learning of its occurrence. Information about all SAEs is collected and recorded on a Serious Adverse Event Report Form. The investigator must assess and record the relationship of each SAE to each specific study treatment (if there is more than one study treatment), complete the SAE Report Form in English, and send the completed, signed form along with the Novartis provided fax cover sheet to the Novartis Oncology Drug Safety and Epidemiology (DS&E) department by fax ([contact]) within 24 hours.

Any additional information for the SAE including complications, progression of the initial SAE, and recurrent episodes must be reported as follow-up to the original episode within 24 hours of the investigator receiving the follow-up information. An SAE occurring at a different time interval or otherwise considered completely unrelated to a previously reported one should be reported separately as a new event.

Any SAEs experienced after a 30 day safety evaluation follow-up period should only be reported to Novartis if the investigator suspects a causal relationship to the study treatment.

Follow-up information is submitted in the same way as the original SAE Report. Each re-occurrence, complication, or progression of the original event should be reported as a follow-up to that event regardless of when it occurs. The follow-up information should describe whether the event has resolved or continues, if and how it was treated, whether the blind was broken or not, and whether the patient continued or withdrew from study participation.

If the SAE is not previously documented in the Investigator's Brochure or Package Insert (new occurrence) and is thought to be related to the Novartis study treatment, an oncology Novartis Drug Safety and Epidemiology (DS&E) department associate may urgently require further information from the investigator for Health Authority reporting. Novartis may need to issue an Investigator Notification (IN), to inform all investigators involved in any study with the same drug that this SAE has been reported. Suspected Unexpected Serious Adverse Reactions (SUSARs) will be collected and reported to the competent authorities and relevant ethics committees in accordance with Directive 2001/20/EC or as per national regulatory requirements in participating countries.

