## **4. RATIONALE**

## 4.1 Study Population

Adult women with definite or probable LAM and impaired lung function will be invited to participate and screened by study inclusion and exclusion criteria below. Definite or probable LAM is established by the ERS LAM guidelines modified by addition of VEGF-D criteria as defined by the MILES Trail (see below). 20 women with LAM and impaired lung function will be enrolled. Many participants will be receiving sirolimus treatment at the time of enrollment; however, sirolimus naïve patients will not be excluded.

Participation of children is not allowed in this study because LAM does not cause clinical disease in this population.

Participation of women and minorities is encouraged, particularly since this disease only affects women. Sirolimus is pregnancy category C and imatinib is pregnancy category D. Pregnancy or intent to become pregnant or nurse during the 2 month study window and for 1 month afterwards is not allowed because of the safety risk of a category D medication. An adequate birth control method during these 3 months will be documented in all women of childbearing potential.

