## 5.4 Visit Schedule

**The Baseline Visit** will begin with signing the informed consent. A history and physical examination, post-bronchodilator spirometry, 6 minute walk test distance, and blood samples will be obtained. Questionnaires will be completed and the patient will be randomized to imatinib mesylate, at an oral dose of 400 mg once daily, or placebo stratified on whether sirolimus has been used in the last month. A sirolimus level and VEGF-D level will be measured.

A 1 week trough sirolimus level and telephone call will be obtained on all subjects entering the study on sirolimus therapy.

**1 Month Visit-** Post-bronchodilator spirometry, 6 minute walk test distance, and blood samples will be obtained. Questionnaires will be completed. Sirolimus will be discontinued if used at baseline.

**2 Month Visit/ End of study-** Post-bronchodilator spirometry, 6 minute walk test distance, and blood samples will be obtained. Questionnaires will be completed. A sirolimus level will be obtained to assure drug cessation. The participant is returned to LAM therapy of their choice.

[figure not shown]

Figure 1. Study Schedule, Stratification and Randomization

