## EQ-5D Health Questionnaire

## 5.5.3 Interim phone calls

A study coordinator will call each participant by phone at 1 week +/- 3 days and 2 weeks +/- 3 days after the baseline visit and again 2 weeks +/- 3 days after the 1 month visit. Phone calls will serve as an opportunity to touch base, inquire about any side effects or adverse events, encourage adherence and confirm the next visit. Completion and results of the phone call will be documented in REDCap.

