#### 6.1.4 Sirolimus side effects

The most common side effects of sirolimus are immune suppression, thrombocytopenia and impaired wound healing. For these reasons, individuals planning surgery (including oral surgery) during the study interval are excluded.

Lung toxicity is a serious complication associated with sirolimus therapy although it usually occurs shortly after beginning therapy. The mechanism of the interstitial pneumonitis is not clear. The toxicity does not appear to be dose dependent, but is more common in patients with underlying lung disease.

Sirolimus also acts on a related complex known as mTORC2. Disruption of mTORC2 produces the diabetes-like symptoms of decreased glucose tolerance and insensitivity to insulin also associated with sirolimus. As with all immunosuppressive medications, in theory sirolimus and imatinib may decrease the body's inherent anticancer activity. However, both of these medications have data that sirolimus can enhance the immune response to tumor targeting and promote tumor regression in clinical trials.

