## **6.3.4 Pregnancy Procedures and Reporting**

Any participant who becomes pregnant during the study will discontinue study medication and procedures for pregnancy follow-up and reporting will be followed:

To ensure patient safety, each pregnancy occurring while the patient is on study treatment must be reported to Novartis within 24 hours of learning of its occurrence. The pregnancy should be followed up to determine outcome, including spontaneous or voluntary termination, details of the birth, and the presence or absence of any birth defects, congenital abnormalities, or maternal and/or newborn complications.

Pregnancy should be reported by the investigator to the Novartis Oncology Drug Safety and Epidemiology Department (DS&E) by fax ([contact]). Pregnancy follow-up should include an assessment of the possible relationship of the pregnancy outcome to the study treatment. Any SAE experienced during pregnancy must be reported on the SAE Report Form.

Because males will not be enrolled in this study, there is no risk of pregnancy in partners of male participants.

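### Serious adverse events are reportable for 30 days after study treatment stops, but no contact is scheduled after the 2 month visit, and the pregnancy reporting duty does not reach the restricted month after the study

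*Combined protocol and SAP*

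**What the plan says.** **SAE window.** Section 6.3.3 requires that every SAE, whatever its suspected cause, from consent "until at least 30 days after the patient has stopped study treatment must be reported to Novartis within 24 hours of learning of its occurrence". Further on, 6.3.3 treats that month as an existing study period: "Any SAEs experienced after a 30 day safety evaluation follow-up period should only be reported to Novartis" where the investigator suspects that study treatment was the cause.

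**Scheduled contacts.** Section 5.1 describes three visits: baseline, 1 month and 2 months. Section 4.4 puts the end of study at 56 days. Section 5.5.3 (Interim phone calls), repeated in 6.4, adds coordinator calls at 1 week and "2 weeks +/- 3 days after the baseline visit and again 2 weeks +/- 3 days after the 1 month visit". Tables 1 and 2 end at 2 months. Of the last visit, section 5.4 says: "The participant is returned to LAM therapy of their choice".

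**Finding adverse events.** Under section 6, participants are told at the start of the study to report adverse changes, and they are asked about events at each visit. The calls in 5.5.3 also ask. Section 6.3.1 follows adverse events until they settle or for up to a month after study completion. Section 6.3 says that the investigators want to record every adverse event, and the safety of imatinib is the third aim in the Specific Aims and in 3.2.

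**Pregnancy.** Section 4.1 says: "Pregnancy or intent to become pregnant or nurse during the 2 month study window and for 1 month afterwards is not allowed", and section 6 repeats it. Both sections promise that birth control will be documented across the three months. Section 5.5.1 and Table 2 place pregnancy tests at the three visits. Section 6.3.4 says that "each pregnancy occurring while the patient is on study treatment must be reported to Novartis within 24 hours", counted from when the site learns of it.

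**The concern.** The protocol defines a post-treatment safety month but schedules nothing in it. The 24-hour reporting clock in 6.3.3 starts when the site learns of an event, and after the 2 month visit no planned step makes the site learn of one. The follow-up in 6.3.1 tracks events and sets no contact to look for new ones.

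What is at stake is the completeness of the safety record. The trial has 20 participants, reports safety descriptively (6.3.1), and is meant to supply safety data for designing a phase 3 study (sections 1 and 2.2). If no event is recorded in the last month, a reader cannot tell whether none occurred or nobody asked.

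The pregnancy provisions have a related gap. The restriction runs for a month after the study because of the risk attached to the study drug, but the duty to report ends with treatment, and the last test is at the 2 month visit.

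**Working it through.** The plan gives no figure to reproduce here. The check lists the scheduled contacts and compares the last one with the end of each window.

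**Inputs**
- Visits: Days 0, 28 and 56 (4.4, 5.1, 5.4).
- Calls: Day 7 ± 3 and Day 14 ± 3 after baseline, and 14 ± 3 days after the 1 month visit, so Day 28 + 14 = Day 42 ± 3 (5.5.3 Interim phone calls, 6.4).
- SAE window: from consent to at least 30 days after stopping study treatment (6.3.3).
- Planned enrolment: 20 (5.2).
- Assumption: the last dose is at the Day 56 visit.

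The 1-week sirolimus level (5.4) falls at the same time as the first call and applies only to participants who enter on sirolimus. It does not change the result.

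**Contacts in order:** Days 0, 7, 14, 28, 42, 56, six in all.

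**Gaps during the study:** 7, 7, 14, 14 and 14 days. The longest nominal gap is 14 days. At the edge of a call window it is 14 + 3 = 17 days.

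**SAE window for a completer**
- Earliest end: 56 + 30 = Day 86.
- Days after the last scheduled contact: 86 − 56 = 30.
- Share of the window: 30 / 86 = 34.9%, about 35%.
- Across 20 completers: 20 × 30 = 600 of 20 × 86 = 1,720 person-days.

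**Early discontinuers.** Their 30 days run from their own stop date. Those who stay in the study keep their remaining visits and calls. For those who leave, 6.4.1 provides an exit interview on withdrawal, whose stated purpose is to settle what happens to their data. No contact is tied to the end of their 30 days.

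**Pregnancy windows side by side**
- Restriction and birth control documentation (4.1 and 6): 2 months + 1 month = 3 months.
- Testing (5.5.1, Table 2): baseline, 1 month and 2 months, with none in the third month.
- Reporting to the drug supplier (6.3.4): on study treatment only.

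A pregnancy that begins in the third month therefore falls inside the restriction but has no scheduled test and no explicit reporting duty under 6.3.4.

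**After the fix.** One contact at 30 days or later after the last dose raises the contacts from 6 to 7 per participant. It cuts the days with no later scheduled contact from 30 to 0.

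**The case against.** The strongest reply is that the gap is narrower than it looks. Events still open at Day 56 are followed for up to a month (6.3.1). Participants are told to report any adverse change (section 6). Some are regular patients of the investigators (5.2), so routine care may bring events to light. This stands, and it rules out saying that events surface only if the participant volunteers them. None of these routes is a scheduled way to find new events in all 20 participants.

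A reader might go further in four ways that the documents do not support.

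- *That the month after Day 56 is one of known high risk.* Section 2.1 reports rapid deterioration after sirolimus was stopped. Here sirolimus stops at the 1 month visit, so that experience bears mainly on the second month, which has a call and a visit with spirometry. It reaches the later month only for those who stay off sirolimus. Section 6.1.4 says of sirolimus lung toxicity that "it usually occurs shortly after beginning therapy". It speaks of beginning treatment, whereas participants who enter on a stable dose (5.3.2) would be resuming it.
- *That about 18 of 20 would restart sirolimus in that month.* This takes 90% of 20. The 90% in section 6 is an estimate for people with LAM and low lung function, while 5.3.1 admits FVC or FEV1 below 90% predicted. For its own sample the plan expects only a majority on rapamycin (2.2, 7.1). Therapy after the study is also each participant's choice.
- *That the pregnancy rules contradict each other.* Sections 4.1 and 6 set a condition of participation; 6.3.4 sets a duty to report to the supplier. Both can be followed. Documented birth control covers the third month, and a congenital anomaly is itself an SAE, reportable after 30 days if causality is suspected. The difference is one of scope.
- *That 35% of events would be missed.* The figure is a share of calendar time and says nothing about event rates.

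Finally, the schedule figure is not shown, the consent pages were removed, and the Manual of Operations mentioned in section 10 was not available. A later contact could be described there. The protocol text and both tables consistently end at 2 months.

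**Conclusion.** The point holds as a mismatch between the reporting window and the schedule. For a completer with the last dose at Day 56, no scheduled visit, call or test covers the final 30 of the 86 days in which SAEs are reportable, and new events in that time reach the site only through spontaneous reports or routine care. This falls short of the stated goal of recording every adverse event.

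The pregnancy reporting duty in 6.3.4 is narrower than the 1-month post-study restriction in 4.1 and section 6, and the sections should be reconciled.

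The consequence is limited to the completeness of the safety data; the primary VEGF-D analysis is not affected. The conclusion rests on the Day 56 last-dose assumption and on there being no further contact in material that could not be seen. It does not depend on the month being unusually risky or on how many participants resume sirolimus.

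**What to change.** In section 5.4, Table 1 and section 5.5.3 (Interim phone calls), add one scripted coordinator call at 30 (+3) days after the actual last dose of study drug. Count from each participant's own stop date, so that early discontinuers who have not withdrawn consent to contact are included. The script asks about new adverse events and SAEs, pregnancy, and LAM therapy taken since the last dose. Log the call in REDCap, as for the existing calls. Repeat the change in 6.4, which restates the call schedule.

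In section 6.3.4, align the pregnancy reporting window with the 1-month post-study restriction in 4.1 and section 6.

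The cost is at most 20 extra calls by the existing coordinators and a short amendment. The downside is that each participant's last contact falls about 30 days later. No dose, clinical rule or efficacy analysis changes.

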## **6.3.4 Pregnancy Procedures and Reporting**

Any participant who becomes pregnant during the study will discontinue study medication and procedures for pregnancy follow-up and reporting will be followed:

To ensure patient safety, each pregnancy occurring while the patient is on study treatment must be reported to Novartis within 24 hours of learning of its occurrence. The pregnancy should be followed up to determine outcome, including spontaneous or voluntary termination, details of the birth, and the presence or absence of any birth defects, congenital abnormalities, or maternal and/or newborn complications.

Pregnancy should be reported by the investigator to the Novartis Oncology Drug Safety and Epidemiology Department (DS&E) by fax ([contact]). Pregnancy follow-up should include an assessment of the possible relationship of the pregnancy outcome to the study treatment. Any SAE experienced during pregnancy must be reported on the SAE Report Form.

Because males will not be enrolled in this study, there is no risk of pregnancy in partners of male participants.

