[name] is a trained study coordinator who will be in charge of creating and maintaining the randomization list at MUSC. [name] is a trained study coordinator who will count and package study medication and placebo for both study sites, so that 10 sets of imatinib and 10 sets of placebo are prepared. [name] [name] will oversee the counting, packaging and sorting as a double check mechanism. [name] will ensure appropriate sorting of correct quantities of imatinb and placebo into two distinct groups. After this double check is complete, [name] will label the two distinct and counted groups (imatinib and placebo) as A and B and [name] will ensure that the labels have been accurately applied to the two distinct groups. Labels compliant with pharmaceutical standard of care will be applied. Five sets of A and 5 sets of B will be sent by FedEx to Columbia University for their 10 participants. At MUSC [name] will randomize the participant without knowledge of whether A and B are drug or placebo. According to the randomization assignment, the blinded assessors, PI [name] or [name] will dispense A or B to the participant. The label will contain space for the authorized blinded dispensing physician to write in the participant's name just prior to dispensing to the participant.

Columbia University will name a trained study team member to perform their randomization. Blinded assessor and co-investigator who will dispense medication at that site is [name]. The Columbia IRB will review and approve their plan and designation.

**Participation of children** is not allowed in this study because LAM does not cause clinical disease in this population.

**Participation of women and minorities** is encouraged, particularly since this disease only affects women. Sirolimus is pregnancy category C and imatinib is pregnancy category D. Pregnancy or intent to become pregnant or nurse during the 2 month study window and for 1 month afterwards is not allowed because of the safety risk of a category D medication. An adequate birth control method during these 3 months will be documented in all women of childbearing potential.

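### Section 6.3.4 ends required pregnancy reporting and follow-up about a month before the protocol's own pregnancy-avoidance period ends, and its two triggers disagree

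*Combined protocol and SAP*

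**What the plan says.** Section 6.3.4 has two triggers in close succession. The opening sentence reads: "Any participant who becomes pregnant during the study will discontinue study medication and procedures for pregnancy follow-up and reporting will be followed". The notification duty that follows is narrower: "each pregnancy occurring while the patient is on study treatment must be reported to Novartis within 24 hours of learning of its occurrence". The next sentence concerns outcome: "The pregnancy should be followed up to determine outcome, including spontaneous or voluntary termination, details of the birth". Its subject is the pregnancy just described, so on its face outcome follow-up carries the narrower, on-treatment condition.

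The protocol sets a longer period elsewhere. Section 4.1 places a bar on pregnancy and nursing, actual or intended: "during the 2 month study window and for 1 month afterwards is not allowed because of the safety risk of a category D medication". Section 6 repeats this and adds: "An adequate birth control method during these 3 months will be documented in all women of childbearing potential".

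Section 6.3.3 gives SAEs a post-treatment period. They are reportable to the supplier from consent "until at least 30 days after the patient has stopped study treatment must be reported to Novartis within 24 hours". After that, "Any SAEs experienced after a 30 day safety evaluation follow-up period should only be reported to Novartis if the investigator suspects a causal relationship". One of the listed SAE criteria is an event that "is a congenital anomaly/birth defect". Section 6.3.1 also follows adverse events for up to 1 month after study completion. The pregnancy rule has no comparable extension.

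**The concern.** The protocol treats the month after the study as risky enough to prohibit pregnancy and to document contraception, yet it does not say what a site must do if a pregnancy begins in that month. A site that learned of one and followed Section 6.3.4 literally could file nothing and follow nothing.

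The SAE rules only partly fill this space. Pregnancy itself is not an SAE, so an uncomplicated pregnancy, or one with a normal outcome, leaves no record by that route. If only adverse outcomes are recorded, there is no denominator to judge them against. Safety of imatinib in LAM is a stated aim (Section 3.2), and Section 6.3 sets the goal of capturing every adverse event. An omission built into the rule therefore matters even when the expected count is very small.

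The two triggers in 6.3.4 are a separate difficulty. Two sites could apply different rules to a woman who has stopped study drug but is still attending visits.

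**Working it through.** This is a comparison of time windows. No sample size, power or error rate bears on it.

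**Inputs.**
- Treatment and study length: 56 days (Sections 4.4, 6.4 and 7.3.1).
- End of study: the 2 month visit (Section 5.4).
- Pregnancy-avoidance period: 2 months plus 1 month (Sections 4.1 and 6).
- SAE reporting to the supplier: to at least 30 days after treatment stops (Section 6.3.3).
- Length of the extra month: not given in days. I assume 30, with a range of 28 to 31.

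**The plan's own figure.** 2 + 1 = 3 months, which agrees with the 3 months of contraception in Sections 4.1 and 6.

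**A completer.** Avoidance period = 56 + extra month. Share outside the pregnancy rule = extra month / avoidance period.

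| Extra month (days) | Avoidance period (days) | Within 6.3.4 | Outside 6.3.4 |
|---|---|---|---|
| 28 | 84 | 56/84 = 66.7% | 28/84 = 33.3% |
| 30 | 86 | 56/86 = 65.1% | 30/86 = 34.9% |
| 31 | 87 | 56/87 = 64.4% | 31/87 = 35.6% |

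For a completer, treatment and study both end at about Day 56, so the wider trigger adds nothing in the extra month.

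**A woman who stops drug early but stays in the study** (30-day month, avoidance period to Day 86):
- Stop at Day 28, on-treatment trigger: 86 - 28 = 58 days outside, 58/86 = 67%.
- Stop at Day 14, on-treatment trigger: 86 - 14 = 72 days outside, 72/86 = 84%.
- Either case, in-study trigger: only the last 30 days outside, 35%.

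The spread between these results measures how far the two triggers disagree.

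**A woman who stops drug and also leaves the study.** Sections 6.4 and 6.4.1 foresee this (withdrawal for side effects; a 10% fall in FEV1 or FVC). Neither trigger then applies. The SAE rule still runs for at least 30 days after her last dose.

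**Which pregnancies fall outside.** A pregnancy that begins on treatment and is discovered later still occurred on treatment and remains reportable. The gap concerns pregnancies that begin after the trigger has lapsed.

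**The case against.** The case against rests on three stronger readings that the documents do not support.

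First, a reader might infer that every woman who stops drug early is uncovered from her last dose. The opening sentence of 6.3.4 applies the follow-up and reporting procedures to any participant who becomes pregnant in the study, so one who stops drug and stays is arguably covered to the 2 month visit. For her, the section only conflicts with itself.

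Second, a reader might infer that a birth defect found late would go unreported unless the investigator suspects causality. That limit applies only to reports to the supplier. Section 6.3.3 separately requires all SAEs to go to the DSMB and obliges the principal investigator to report them to the FDA and IRB, with no time limit stated there. Section 6.3.4 also puts any SAE during pregnancy on the SAE form. These routes still depend on the site hearing of the event, and they do not record an uncomplicated pregnancy.

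Third, a reader might treat each such pregnancy as an unreported drug exposure. Section 6 provides 10 sets of imatinib and 10 of placebo, so only some would be potential exposures. The 35% is a share of calendar days, not of exposure or risk.

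The practical objection also has force. No visit (Section 5.1) or call (Section 5.5.3, interim phone calls) is planned after the 2 month visit, so a wider rule would reach only pregnancies the site happens to learn of. Section 6.1 refers to a consent form that was not available here, and it may instruct participants further. Neither point tells a site what to do with a pregnancy it knows about.

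**Conclusion.** The point holds in limited form. Section 6.3.4 contains two conflicting triggers, and for a completer neither reaches the final month in which Sections 4.1 and 6 still bar pregnancy: about 30 of 86 days, 35% (33% to 36%). A pregnancy beginning then, or in a woman who has both stopped drug and left the study early, has no required report or outcome follow-up unless an SAE arises. For a woman who stops drug but remains in the study, the finding is only that the section is internally inconsistent.

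This rests on reading the 2 month visit as the end of the study, on a month of 28 to 31 days, and on reading the outcome sentence as referring to the on-treatment pregnancy. Few or no events are expected among 20 women, and the efficacy analysis is unaffected. It is a modest gap in safety capture, worth correcting because the correction costs so little. I take no view on how long the clinically right period is, only that the passages must agree.

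**What to change.** Reconcile Sections 4.1, 6, 6.3.3 and 6.3.4. In 6.3.4, state once the window for pregnancy reporting and outcome follow-up. Make it no shorter than the protocol's own pregnancy-avoidance period and no narrower than either existing trigger, and say that it also applies to women who have stopped drug or left the study. State that outcome follow-up covers every pregnancy in that window. Keep the instruction on stopping study medication as a separate sentence, unchanged.

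Replacing both triggers with a period counted only from the last dose would not do this. For a woman who stops at Day 14, a 30-day period ends at 14 + 30 = Day 44. That is 12 days before the Day 56 visit to which the opening sentence now arguably covers her, and 42 days before Day 86.

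The cost is a sentence or two in 6.3.4, matching consent text if the consent form repeats the rule, and at most one or two extra report forms. No visit, test or contact is added.
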